#### **5.5.2. Prohibited Medications and Therapies**

Subjects who start prohibited medications or therapies at any time during the study will be considered treatment failures for analysis (ie, non-responders) and must be withdrawn from study agent and return for an Exit visit 4 weeks after the last administration of study agent and a follow-up visit 8 weeks after the last administration of study agent. In addition, an attempt will be made to ascertain survival status approximately 52 weeks after the first dose of study agent.

The following medications and therapies are prohibited at any time during the study:

- Other investigational agents (biologic or non-biologic). Investigational applies to any drug not approved for sale in the country in which it is being used.
- Co-enrollment into another study of an investigational agent or another study that may interfere with the conduct of this protocol.
- Anti-TNF therapy (eg, adalimumab, certolizumab pegol, etanercept, golimumab, infliximab).
- Other biologics (eg, rituximab, abatacept, interleukin-1 receptor antagonist [anakinra], tocilizumab).
- Intravenous immunoglobulin (IVIG).
- IV cyclophosphamide.
- Plasmapheresis

### **5.5.3. Live Vaccines**

Live vaccines are not permitted in the study. Subjects who require a live vaccine during the study should have study agent discontinued prior to receiving the live vaccine.

## **6. STUDY PROCEDURES**

The nature of potential risks and benefits associated with participation in the study will be explained to all potential study subjects. Written informed consent (including consent for the use and disclosure of research-related health information) must be obtained before the subject can begin any screening procedures that are not considered part of standard patient care.

Subjects participating in the pharmacogenetics (PGx) research portion of the protocol must sign the PGx informed consent prior to any PGx samples being drawn from the subject.

The FACIT-Fatigue Scale will only be completed by subjects for whom a survey exists in the subject's language.

Refer to the Study Calendar ([Table 6-1](#)), Study Procedures Manual, and Central Laboratory Manual for additional information.

### **6.1. Screening Procedures (Day -35 to Day 0)**

Subjects must be on appropriate stable standard therapy before entering the trial (see Inclusion Criteria Section [4.1](#) and Section [5.5.1](#)). Investigators should consider this carefully before screening subjects that only recently came under their care. A 60-day observation period is suggested if previous SLE disease activity documentation is suboptimal. This period prior to screening allows the principal investigator to observe the subject and make any necessary medication adjustments, especially if a subject has been recently referred to the study site.

The following assessments are required at screening:

- Demographics (including self-identified race).
- Medical history.
- Weight
- Complete physical examination.
- Confirm diagnosis of SLE disease (based on ACR criteria) by reviewing previously documented clinical records (see [Appendix 1](#)).
- Record concurrent medications
- Blood samples for: (see [Appendix 10 – Laboratory Tests](#))
  - Hematology.
  - Modified Chem 20 (non-fasting).
  - Serum pregnancy test - for all women with an intact uterus, unless exempted from pregnancy testing (ie, of non-childbearing potential - women who had a hysterectomy, are post-menopausal which is defined as 1 year without menses, have both ovaries surgically removed, or have current documented tubal ligation or any other permanent female sterilization procedure).
  - HIV antibody, HBsAg, HB core antibody, and hepatitis C antibody testing.
  - Biological markers (Complement C3, C4).
  - Serum immunoglobulin isotypes (IgG, IgM, IgA).
  - Autoantibodies (ANA and anti-dsDNA).
- Urine sample for:
  - Routine urinalysis.
  - Alcohol and drug screen.
  - Spot urine for macroscopic/microscopic/proteinuria assessments.
- Disease activity scales:
  - SELENA SLEDAI (see [Appendix 5](#); refer to Section [6.8.1](#) Guidelines for Scoring Proteinuria).
    - Confirm SLE disease is active, defined as SELENA SLEDAI score  $\geq 8$  at screening.
  - Physician's Global Assessment (PGA) (see [Appendix 5](#)).
  - SLE Flare Index (see [Appendix 5](#)).
  - BILAG (see [Appendix 7](#)).
- Suicidality assessment by using the Columbia-Suicide Severity Rating Scale (C-SSRS) Baseline/Screening assessment form (see [Appendix 3](#) and Section [7.5](#)) at screening.
- Confirm subject meets study entry criteria.

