**NOTE:**

- Pre-existing SLE medications must be stable for at least 30 days prior to Day 0.
- Corticosteroids may be added as new medication or their doses adjusted only up to 30 days prior to Day 0 (see Exclusion Criterion #6).
- New SLE therapy other than corticosteroids must not be added within 60 days of Day 0 (see Exclusion Criterion #5).

7. A female subject is eligible to enter the study if she is:

- Not pregnant or nursing;
- Of non-childbearing potential defined as

- pre-menopausal females with a documented tubal ligation, hysterectomy, documented hysteroscopic tubal occlusion procedure with follow-up confirmation of bilateral tubal occlusion, or documented bilateral oophorectomy or
- postmenopausal defined as 12 months of spontaneous amenorrhea with an appropriate clinical profile [eg, > 45 years, in the absence of hormone replacement therapy or other cause for amenorrhea]; in questionable cases obtain a blood sample for follicle stimulating hormone (FSH) and estradiol simultaneously to confirm. Diagnostic levels for FSH and estradiol vary by specific laboratories/assays;
- OR is of child-bearing potential with negative pregnancy test as determined by serum human chorionic gonadotrophin (hCG) test at screening and urine hCG test prior to dosing AND
  - Agrees to use one of the contraception methods listed in the protocol (see Section 4.3) for 2 weeks prior to the day of dosing to sufficiently minimize the risk of pregnancy at that point. Female subjects must agree to use contraception until 16 weeks following the last dose of study agent.
- OR has only same-sex partners, when this is her preferred and usual lifestyle.

8. Have the ability to understand the requirements of the study, provide written informed consent (including consent for the use and disclosure of research-related health information), and comply with the study protocol procedures (including required study visits).

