### **5.3. Dose, Route of Administration, and Schedule**

The treatment groups consist of one active treatment arm (10 mg/kg belimumab) and a placebo arm, with both treatment groups receiving standard therapy. All study agent treatments will be administered IV over no less than 1 hour. Once randomized, subjects will be dosed with study agent on Days 0, 14, and 28 and every 28 days thereafter through 48 weeks of treatment. Subjects who complete the initial treatment period (48 weeks of treatment with final assessment at Week 52) will be given the option to receive belimumab in the 6-month open-label extension phase.

Premedication including an antihistamine, with or without an antipyretic, may be administered before the infusion. Antihistamine H2-receptor antagonists (eg, ranitidine) are also permitted.

Study agent should be administered by investigators/site personnel prepared to manage infusion reactions and anaphylaxis. The infusion rate may be slowed or interrupted if the subject develops an infusion reaction. Investigators/site personnel should be aware of the risk of hypersensitivity reactions, which may present as infusion reactions, and monitor subjects closely. In the event of a serious reaction, study agent administration must be discontinued immediately and the appropriate medical therapy administered.

In the post-marketing setting, delayed onset of symptoms of acute hypersensitivity reactions has been observed. Subjects should remain under clinical supervision for 3 hours after completion of the first 2 infusions in the double-blind treatment phase and the 6-month open-label extension. Should symptoms of acute hypersensitivity occur, an extended period of monitoring may be appropriate, based on clinical judgment. This may include, but is not limited to, monitoring vital signs and observing any untoward reactions. In addition, delayed-type, non-acute hypersensitivity reaction have also been observed and included symptoms such as rash, nausea, fatigue, myalgia, headache, and facial edema. Beyond the first 2 infusions, subjects should be monitored during and for an appropriate period of time after infusion according to the study sites' guidelines or standard operating procedure for IV infusions.

Subjects should be made aware of the potential risk, the signs and symptoms of such reactions, and the importance of immediately seeking medical attention. For further information, see the belimumab IB.

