**Table 6-1      Study calendar - On-treatment evaluations (footnotes)**

Refer to Section 6.1 for a list of assessments required for screening/eligibility.

- A The Exit (Day 364) visit will occur approximately 4 weeks after the last dose of study agent. For subjects completing all 48 weeks of treatment and continuing into the 6-month open-label extension, this visit will also serve as their 1st (ie, Day 0) visit of the 6-month open-label extension (see Table 6-2). For subjects who discontinue study agent prior to Week 48, the Exit (Day 364) visit should be performed 4 weeks after the last administration of study agent and a follow-up visit 8 weeks after the last administration of study agent, and a survival assessment (eg, by phone contact) will take place approximately 52 weeks after the first dose of study agent (see Footnote N).
- B The 8-week follow-up visit is to occur approximately 8 weeks after last dose of study agent for subjects withdrawing early and those subjects who do not continue into the 6-month open-label extension.
- C Must be completed by the subject prior to any study-related discussion with the investigator or study coordinator. The FACIT-Fatigue Scale will only be completed by subjects for whom a survey exists in the subject's language.
- D Weight should be obtained prior to dosing at each visit to calculate the dose to be administered. At sites where it is impractical to use the subject's current body weight to calculate the dose, it is permissible to use the subject's body weight from the previous visit. However, the subject's body weight will be measured prior to dosing and if the previous visit weight and current visit weight vary by more than 10% then the weight measured at the current visit must be used.
- E Refer to Appendix 10 for a listing of laboratory assessments to be completed. PT/PTT will be assessed according to the separate line item for PT/PTT in this table.
- F A 24-hour urine may be done if clinically indicated (eg, renal flare).
- G Serum pregnancy test required at screening. Results of urine pregnancy test at subsequent visits, if required, must be available prior to dose. See Section 6.1 (Screening Procedures) for definition of those exempted from subsequent pregnancy testing. Women of child-bearing potential must be reminded of the requirement to report any pregnancy that occurs through 16 weeks following the last dose of study agent (see Section 7.6).

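### Section 6.1 exempts women from on-treatment pregnancy testing on a looser definition than inclusion criterion 7, and Table 6-1 footnote G relies on it alone for 13 of the 14 double-blind infusions

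*Protocol*

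**What the plan says.** Criterion 7 in Section 4.1, repeated in the Synopsis, defines non-childbearing potential in two ways. The first is a listed surgical route, which includes a "documented hysteroscopic tubal occlusion procedure with follow-up confirmation of bilateral tubal occlusion". The second is menopause, worded as "postmenopausal defined as 12 months of spontaneous amenorrhea with an appropriate clinical profile". Its examples of a suitable profile are age over 45 and amenorrhea "in the absence of hormone replacement therapy or other cause for amenorrhea". In questionable cases FSH and estradiol are to be measured together. A woman of childbearing potential may enter only with a "negative pregnancy test as determined by serum human chorionic gonadotrophin (hCG) test at screening and urine hCG test prior to dosing".

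Section 6.1 requires a serum pregnancy test at screening for all women with an intact uterus unless exempted. It uses the same label, non-childbearing potential, but then spells out its own definition and does not cite Section 4.1 for it. The exempted women include those who "are post-menopausal which is defined as 1 year without menses" and those who "have current documented tubal ligation or any other permanent female sterilization procedure".

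Table 6-1 schedules a pregnancy test at every double-blind visit. Footnote G says that urine results at later visits, where required, must be available before the dose, and then: "See Section 6.1 (Screening Procedures) for definition of those exempted from subsequent pregnancy testing". It does not name Section 4.1.

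**The concern.** Section 6.1 drops the conditions that make a year of amenorrhea evidence of menopause: that it be spontaneous, that the clinical profile fit, and that hormones be checked when there is doubt. Amenorrhea caused by drugs or hormones passes the Section 6.1 wording and fails criterion 7. Because footnote G cites only Section 6.1, the looser wording is the stated rule for who is tested on treatment.

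The stake is subject safety. Pregnancy is a reason for withdrawal in Section 6.9. A woman who is wrongly exempted could go on receiving infusions after conceiving, with recognition, withdrawal and reporting all delayed. The case is not far-fetched: Section 1.1 puts women at about 90% of SLE patients, with onset generally between ages 20 and 40.

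**Working it through.** No power or alpha figure is involved. The check compares the texts and counts infusions.

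**Definitions side by side**

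| Element | Section 4.1, criterion 7 | Section 6.1 |
|---|---|---|
| Duration of amenorrhea | 12 months | 1 year |
| Must be spontaneous | Yes | Not stated |
| Clinical profile | Required (age and absence of hormone therapy or other cause given as examples) | Not stated |
| FSH and estradiol | In questionable cases | Not stated |
| Tubal occlusion or other sterilization | Hysteroscopic occlusion needs follow-up confirmation | Any other permanent procedure; confirmation not mentioned |

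The durations agree; the conditions do not. The amenorrhea rows are a plain conflict. The sterilization row is weaker: Section 6.1 is less explicit and leaves open whether an unconfirmed occlusion counts as permanent.

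**Test case.** Take a woman of 30 with 14 months of drug-induced amenorrhea (illustrative values). Under criterion 7 her amenorrhea is not spontaneous, so she is of childbearing potential and needs negative serum and urine hCG tests to enter. Under Section 6.1 she has had more than 1 year without menses, so read literally she is exempt.

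**Infusions affected.** Section 5.3 states that "subjects will be dosed with study agent on Days 0, 14, and 28 and every 28 days thereafter through 48 weeks of treatment".

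- Days 0 and 14: 2 infusions.
- Every 28 days from Day 28 to Day 336: 336 / 28 = 12 infusions.
- Total: 2 + 12 = 14 double-blind infusions.
- Criterion 7 separately requires the urine test before the Day 0 dose. That leaves 14 − 1 = 13 infusions, Day 14 to Day 336, for which only footnote G with Section 6.1 says who is exempt.

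**Longest interval.** From the Day 0 test to the last double-blind infusion: 336 − 0 = 336 days, and 336 / 7 = 48 weeks.

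The open-label infusions are not counted. Footnote c of Table 6-2 asks for a urine test as required and contains no conflicting exemption.

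**Likely origin.** The Amendment 02 change log shows that the Section 6.1 wording matches the definition that amendment replaced in criterion 7. The only change logged for the Section 6.1 screening blood tests concerns hepatitis B. This suggests an update that was not carried through. The finding itself rests on the current Sections 4.1 and 6.1 and footnote G.

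**The case against.** The strongest reply is that the harm needs an unlikely sequence at the site. Section 6.1 exempts women of non-childbearing potential, and that status is settled at entry under criterion 7. A site would have to classify a woman as of childbearing potential, test her and impose contraception, then treat her as exempt from Day 14. The shared label makes this less likely. It does not prevent it, because Section 6.1 gives its own definition and footnote G names that section.

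Other safeguards remain. Section 4.3 requires abstinence or a method with a failure rate below 1%, with an additional method for women who take mycophenolate with an oral contraceptive. Footnote G requires that women of childbearing potential be reminded to report a pregnancy. Examination and adverse event review continue on treatment. These points stand and keep the residual risk small.

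The urine test in criterion 7 could also be read as applying before every dose. Its place among the entry criteria favors Day 0. On the wider reading, criterion 7 and footnote G would contradict each other directly, and the same repair would be needed.

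Three limits are fair. Age over 45 and absence of hormone therapy are examples in criterion 7, so the firm differences are spontaneity, the need for a suitable profile and the hormone check. The sterilization wording is an ambiguity only. And Section 6.1 is not looser throughout: it does not exempt women with only same-sex partners, whom criterion 7 admits by a route with no hCG condition attached.

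**Conclusion.** The concern holds. Two current texts disagree on who is of non-childbearing potential, and the looser one is the only rule cited for testing after entry. For an affected woman, up to 13 of 14 double-blind infusions, over up to 336 days, could be given without a required pregnancy test.

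This is a ceiling. It assumes a literal reading of Section 6.1 at every visit, and the Day 0 reading of the urine test in criterion 7. The protocol gives no figure from which to estimate how many such women would enroll; the number is probably small. No endpoint, sample size or efficacy analysis is touched. It should still be corrected, because it is an operative safety rule that is wrong as written.

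**What to change.** In Section 6.1, replace the parenthesis that defines the exempted women with a cross-reference to the definition of non-childbearing potential in Section 4.1, criterion 7. Refer to that definition specifically, not to criterion 7 as a whole, so that the same-sex-partner route does not become a testing exemption by accident. In Table 6-1, point footnote G to Section 4.1 in place of Section 6.1. Adding the same pointer to footnote c of Table 6-2 is optional tidying.

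The cost is wording in two places, or three with the optional one, and a few extra urine tests.

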## **6.2. Study Enrollment Procedures**

Subjects who have undergone all screening procedures and have met the entry criteria will be enrolled into the study and assigned to treatment by Interactive Web or Voice Response System (IWRs/IVRS). Subjects will be randomized in a 2:1 ratio to treatment with either 10 mg/kg belimumab or placebo. At randomization, subjects will be stratified

by their screening SELENA SLEDAI score (8-9 vs  $\geq$  10), complement level (C3 and/or C4 low vs other), and region (US/Canada vs rest of the world).

### **6.3. Double-Blind Treatment Period**

Subjects will be evaluated at the study site during the scheduled study visits outlined in the Study Calendar in [Table 6-1](#). On Day 0, the subject will be randomized and receive the 1st dose of study agent. After the 1st month of therapy, visits to the study site for clinical evaluation, disease activity assessment, and laboratory sampling will occur approximately every 28 days (calculated from the Day 0 dose) for a total of 48 weeks of treatment. All efforts should be made to retain subjects on schedule, based on the date of their Day 0 dose.

The final efficacy evaluation will occur at Week 52 (ie, the Day 364/Exit visit, approximately 4 weeks after the last dose of study agent).

Time windows are provided for each study visit after Day 0 in [Table 6-1](#) to allow flexibility in site and subject scheduling. All study visits should occur within the visit window of the scheduled study visit (see [Table 6-1](#)).

All subjects who withdraw from treatment prior to Week 52 will be followed (eg phone contact) for survival approximately 52 weeks after the first dose of study agent. In the event that a subject withdraws consent, an attempt should be made at the time of consent withdrawal to obtain consent for survival status.

Subjects who complete the double-blind period through Day 364 (Week 52) will be given the option to receive belimumab in the 6-month open-label extension.

- Subjects who complete the 364 day (52-week) double-blind period, but do not enter the open-label extension, will not have study agent administered at Week 52. Assessments should be completed for the Day 364/Week 52 visit, and then the subject should return in 4 weeks for the 8-week Follow-up Visit.
- Subjects who wish to continue in the open-label extension, will have study agent administered at the Day 364 (Week 52/Day 0 of open-label extension) visit after all Day 364 (Week 52) assessments are performed (refer to [Table 6-1](#) below).

This is an on-treatment Study Calendar. Please refer to Section 6.1 for a complete list of assessments required during screening.

**Table 6-1 Study calendar- On-treatment evaluations**

		52-Week Double-Blind Treatment Period Days 0-364 (Weeks 0-52)														Post-Treatment Follow-up Period						
		Screening	Day 0 visit	Day 14 visit ± 3 days	Day 28 visit ± 3 days	Day 56 visit ± 7 days	Day 84 visit ± 7 days	Day 112 visit ± 7 days	Day 140 visit ± 7 days	Day 168 visit ± 7 days	Day 196 visit ± 7 days	Day 224 visit ± 7 days	Day 252 visit ± 7 days	Day 280 visit ± 7 days	Day 308 visit ± 7 days	Day 336 visit ± 7 days	Day 364/ EXIT (4-wks post dose) A, J ± 7 days	Post-txt f-up for non-completers ± 7 days	8-week Follow-up B ± 7 Days	Unscheduled Visit L		
Study Day			Wk 2	Wk 4	Wk 8	Wk 12	Wk 16	Wk 20	Wk 24	Wk 28	Wk 32	Wk 36	Wk 40	Wk 44	Wk 48	Wk 52	4 wks post last dose					
Study Week																						
Written Informed Consent	X																					
Demographics (including race)	X																					
Medical History and complete Physical Exam	X																					
SLE History/diagnosis	X																					
Eligibility Criteria	X																					
Clinical Assessments:																						
Weight D	X	X	X	X	X	X	X	X	X	X	X	X	X	X	X	X	X					
Symptom-driven Physical Exam		X		X	X	X	X	X	X	X	X	X	X	X	X	X	X		X	X		
C-SSRS Baseline/Screening I	X																					
C-SSRS Since Last Visit I		X	X	X	X	X	X	X	X	X	X	X	X	X	X	X	X		X			
Adverse Events		X	X	X	X	X	X	X	X	X	X	X	X	X	X	X	X		X	X		
Record all current medications	X	X	X	X	X	X	X	X	X	X	X	X	X	X	X	X	X		X	X		

**Table 6-1 Study calendar- On-treatment evaluations**

Study Day	Screening	52-Week Double-Blind Treatment Period Days 0-364 (Weeks 0-52)														Post-Treatment Follow-up Period				
		Day 0 visit	Day 14 visit ± 3 days	Day 28 visit ± 3 days	Day 56 visit ± 7 days	Day 84 visit ± 7 days	Day 112 visit ± 7 days	Day 140 visit ± 7 days	Day 168 visit ± 7 days	Day 196 visit ± 7 days	Day 224 visit ± 7 days	Day 252 visit ± 7 days	Day 280 visit ± 7 days	Day 308 visit ± 7 days	Day 336 visit ± 7 days	Day 364/ EXIT (4-wks post dose) A,J ± 7 days	Post-txt f-up for non-completers ± 7 days	8-week Follow-up B ± 7 Days	Unscheduled Visit L	
Study Week		Wk 2	Wk 4	Wk 8	Wk 12	Wk 16	Wk 20	Wk 24	Wk 28	Wk 32	Wk 36	Wk 40	Wk 44	Wk 48	Wk 52	4 wks post last dose				
SLE Disease Activity Scales K	X	X		X	X	X	X	X	X	X	X	X	X	X	X					
SLICC/ACR Damage Index		X														X				
FACIT-Fatigue Scale C		X		X	X	X			X		X				X					
Survival assessment N																	X			
Laboratory Assessments:																				
HIV, Hepatitis B and Hepatitis C serology	X																			
Alcohol and Drug Screen	X																			
Labs: Hematology & Modified Chem 20 (non-fasting) E	X	X	X	X	X	X	X	X	X	X	X	X	X	X	X			X	X	
PT/PTT E	X	X			X				X									X		
Urinalysis	X	X		X	X	X	X	X	X	X	X	X	X	X	X	X	X	X	X	
Spot urine (protein to creatinine ratio) F	X	X		X	X	X	X	X	X	X	X	X	X	X	X	X			X	
Pregnancy Test G	X	X	X	X	X	X	X	X	X	X	X	X	X	X	X	X	X	X	X	
Pharmacokinetic Sampling H		X	X			X			X							X		X	X	

